8.6.1.6 Duration of Response (DOR)

Subjects who achieved CR or PR and are alive, have not progressed, have not initiated new anti-cancer treatment, have not missed ≥ 2 consecutive disease assessments and have not been determined to be lost to follow-up are considered ongoing responders at the time of analysis.

Protocol/Amendment No.: 394-06

The non-parametric Kaplan-Meier method will be used to estimate the DOR curve in each treatment group; estimates and 95% CIs at specific duration time points will be provided.

Censoring rules for DOR are summarized in Table 11.

Table 11 Censoring Rules for DOR

Situation	Date of Progression or Censoring	Outcome
No progression nor death, no new anti-cancer therapy initiated	Last adequate disease assessment	Censor (non-event)
No progression nor death, new anti- cancer therapy initiated	Last adequate disease assessment before new anti-cancer therapy initiated	Censor (non-event)
Death or progression after ≥2 consecutive missed adequate disease assessments or after new anti-cancer therapy	Earlier date of last adequate disease assessment prior to ≥2 missed adequate disease assessments and new anti-cancer therapy, if any	Censor (non-event)
Death or progression after ≤1 missed adequate disease assessments and before new anticancer therapy, if any	PD or death	End of response (Event)

Subjects are considered to have an ongoing response if censored, alive, have not progressed, have not started a new anti-cancer therapy, have not missed ≥ 2 consecutive disease assessments, and have not been determined to be lost to follow-up.

Table 12 summarizes the primary analysis approach for key efficacy endpoints. Sensitivity analysis methods are described above for each endpoint.

Analyses of the DCR, TTP, and DOR data will be performed at the time of the interim and final analyses of OS.

The strategy to address multiplicity issues with regard to multiple efficacy endpoints, multiple populations, and interim analyses is described in Section 8.7 Interim Analyses and in Section 8.8 Multiplicity.

Protocol/Amendment No.: 394-06

Table 12 Analysis Strategy for Key Efficacy Hypotheses

Endpoint/Variable (Description, Time Point)	Statistical Method [†]	Analysis Population	Missing Data Approach
Primary Hypothesis			
OS	Test: Stratified Log- rank test Estimation: Stratified Cox model with Efron's tie handling method.	ITT	Censored at the last date the subject was known to be alive
Secondary Endpoints	l		
PFS per RECIST 1.1 by BICR	Test: Stratified Log- rank test Estimation: Stratified Cox model with Efron's tie handling method	ITT	Primary censoring rule Sensitivity analysis 1 Sensitivity analysis 2 (More details are in Table 9)
ORR per RECIST 1.1 by BICR	Stratified M & N method [‡]	ITT	Subjects with missing data are considered non-responders

[†] Statistical models are described in further detail in the text. For stratified analyses, the stratification factors applied to the analysis model will be: macrovascular invasion (Yes, No), α-fetoprotein (ng/mL) (<200, ≥200) and region (China, ex-China), with all cells that correspond to macrovascular invasion=Yes combined.

8.6.2 Statistical Methods for Safety Analyses

Safety and tolerability will be assessed by clinical review of all relevant parameters including adverse events (AEs), laboratory tests, and vital signs.

Tiered Approach

The analysis of safety results will follow a tiered approach (Table 13). The tiers differ with respect to the analyses that will be performed. For this protocol, there are no Tier 1 events.

Tier 2 parameters will be assessed via point estimates with 95% confidence intervals provided for between-group comparisons; only point estimates by treatment group are provided for Tier 3 safety parameters.

AEs (specific terms as well as system organ class terms) will be classified as belonging to "Tier 2" or "Tier 3", based on the number of events observed. Membership in Tier 2 requires that at least 4 subjects in any treatment group exhibit the event; all other AEs and predefined limits of change will belong to Tier 3.

The threshold of at least 4 events was chosen because the 95% confidence interval for the between-group difference in percent incidence will always include zero when treatment groups of equal size each have less than 4 events and thus would add little to the interpretation of potentially meaningful differences. Because many 95% confidence intervals may be provided without adjustment for multiplicity, the confidence intervals should be

Miettinen and Nurminen method.

Protocol/Amendment No.: 394-06

regarded as a helpful descriptive measure to be used in review, not a formal method for assessing the statistical significance of the between-group differences in AEs and predefined limits of change.

Continuous measures such as changes from baseline in laboratory values and vital signs, that are not pre-specified as Tier-1 endpoints will be considered Tier 3 safety parameters. Summary statistics for baseline, on-treatment, and change from baseline values will be provided by treatment group in table format.

In addition, the broad clinical and laboratory AE categories consisting of the percentage of subjects with any AE, any drug related AE, any Grade 3-5 AE, any serious AE, any AE which is both drug-related and Grade 3-5, any AE which is both serious and drug-related, dose modification due to AE, and who discontinued due to an AE, and death will be considered Tier 2 endpoints.

The 95% confidence intervals will be provided for between- treatment differences in the percentage of subjects with Tier 2 events; these analyses will be performed using the Miettinen and Nurminen method [55], an unconditional, asymptotic method. Safety analyses will not be stratified.

 Table 13
 Analysis Strategy for Safety Parameters

Safety Tier	Safety Endpoint [†]	95% CI for Treatment Comparison	Descriptive Statistics
Tier 2	Any AE	X	X
	Any Serious AE	X	X
	Any Grade 3-5 AE	X	X
	Any Drug-Related AE	X	X
	Any Serious and Drug-Related AE	X	X
	Any Grade 3-5 and Drug-Related AE	X	X
	Dose Modification due to AE	X	X
	Discontinuation due to AE	X	X
	Death		
	Specific AEs, SOCs, or PDLCs [‡] (incidence ≥4 of subjects in one of the treatment groups)	X	X
Tier 3	Specific AEs, SOCs or PDLCs [‡] (incidence <4 of subjects in all of the treatment groups)		X
	Change from Baseline Results (Labs, ECGs, Vital Signs)		X

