2.0 TRIAL DESIGN

2.1 Trial Design

This is a double-blind randomized phase III trial of pembrolizumab plus best supportive care (BSC) versus placebo plus BSC in Asian subjects with previously systemically treated advanced hepatocellular carcinoma (HCC). To be eligible, subjects must have documented objective radiographic progression of disease (PD) on or after stopping treatment with sorafenib or oxaliplatin-based chemotherapy, or else be intolerant of sorafenib or oxaliplatinbased chemotherapy as defined in Section 5.1.2. They also must have disease not amenable to a curative treatment approach (e.g., transplant, surgery, or ablation). In order to be eligible, subjects must have at least one measurable lesion that is confirmed by the investigator per Response Evaluation Criteria in Solid Tumors (RECIST) 1.1 prior to randomization. Subjects will be enrolled regardless of tissue programmed death ligand 1 (PD-L1) biomarker status. Subjects will not be required to provide a tumor tissue sample for biomarker analysis, but are strongly urged to do so if tissue is available. Available samples will be evaluated at a central laboratory for expression status of PD-L1 by immunohistochemistry (IHC). Approximately 450 subjects will be randomized at a 2:1 ratio to receive pembrolizumab 200 mg intravenously (IV) every 3 weeks (Q3W) or placebo (IV administration of saline) Q3W. Subjects from both arms can receive BSC as per local standard of care.

The primary objective of this trial is to compare the overall survival (OS) in subjects who receive pembrolizumab plus BSC and those who receive placebo plus BSC. On-study imaging assessments will be performed Q6W calculated from the date of randomization and independent of treatment delays. RECIST 1.1 will be used by the site for treatment decisions until the first radiologic evidence of progressive disease (PD).

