5.3 Randomization

Treatment allocation/randomization will occur centrally using an interactive voice response system / integrated web response system (IVRS/IWRS). There are 2 treatment arms. Subjects will be assigned randomly in a 2:1 ratio to pembrolizumab and placebo, respectively.

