8.4.2 Safety Endpoints

Safety measurements are described in Section 4.2.3.4 Safety Endpoints and Section 7.

Safety and tolerability will be assessed by clinical review of all relevant parameters including adverse events (AEs), laboratory tests, and vital signs. Safety parameters to be analyzed include, but are not limited to, AEs, SAEs, fatal AEs, and laboratory changes. Furthermore, specific events will be collected and designated as events of clinical interest (ECIs) as described in Section 7.2.3.

Events of clinical interest for this trial include:

- 1. An overdose of Sponsor's product, as defined in Section 7.2.1 Definition of an Overdose for This Protocol and Reporting of Overdose to the Sponsor, that is not associated with clinical symptoms or abnormal laboratory results.
- 2. Hepatic ECIs as defined in Section 7.2.3.

There are no "Tier 1" events in this trial. In addition, the broad clinical and laboratory AE categories consisting of the percentage of subjects with any AE, any drug related AE, any Grade 3-5 AE, any serious AE, any AE which is both drug-related and Grade 3-5, any AE which is both serious and drug-related, dose modification due to AE, and who discontinued due to an AE, and death will be considered Tier 2 endpoints. AEs (specific terms as well as system organ class terms) will be classified as belonging to "Tier 2" or "Tier 3", based on the number of events observed. Membership in Tier 2 requires that at least 4 subjects in any treatment group exhibit the event; all other AEs and predefined limits of change will belong to Tier 3.

Protocol/Amendment No.: 394-06

Analysis Populations

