8.5.2 Safety Analysis Populations

The All Subjects as Treated (ASaT) population will be used for the analysis of safety data in this study. The ASaT population consists of all randomized subjects who received at least one dose of study treatment. Subjects will be included in the treatment group corresponding to the study treatment they actually received for the analysis of safety data using the ASaT population. For most subjects this will be the treatment group to which they are randomized. Subjects who take incorrect study treatment for the entire treatment period will be included in the treatment group corresponding to the study treatment actually received. Any subject who receives the incorrect study medication for one cycle but receives the correct treatment for all other cycles will be analyzed according to the randomized treatment group and a narrative will be provided for any events that occur during the cycle for which the subject is incorrectly dosed.

At least one laboratory or vital sign measurement obtained subsequent to at least one dose of study treatment is required for inclusion in the analysis of each specific parameter. To assess change from baseline, a baseline measurement is also required.

Details on the approach to handling missing data for safety analyses are provided in Section 8.6 Statistical Methods.

8.6 **Statistical Methods**

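### The 4-subject cut for showing between-arm safety intervals is justified only for equal arms; at 2:1 it leaves out two placebo-excess patterns whose intervals exclude zero (minor)

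*Protocol*

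**What the plan says.** Protocol 8.4.2 sets the rule for specific terms, system organ classes and predefined limits of change: "Membership in Tier 2 requires that at least 4 subjects in any treatment group exhibit the event". Everything else is Tier 3, and Protocol 8.6.2 says that "only point estimates by treatment group are provided for Tier 3 safety parameters".

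The only reason offered for the number 4 is in the same section: the 95% interval for the difference "will always include zero when treatment groups of equal size each have less than 4 events". On the method, "these analyses will be performed using the Miettinen and Nurminen method", and "Safety analyses will not be stratified".

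The arms are not of equal size. Protocol 5.3 states: "Subjects will be assigned randomly in a 2:1 ratio to pembrolizumab and placebo, respectively".

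SAP 3.4.2 repeats the count rule, and SAP 3.5.2 repeats both the rule and its reason. SAP Table 5, in the same Section 3.5.2, uses percentages instead. A term is Tier 2 at 10% or more (any AE), 2% or more (Grade 3-5) or 1% or more (serious) in one group, and specific terms are Tier 3 below 4% in all groups. SAP Section 2 describes Table 5 as a short list of Tier 2 events.

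**The concern.** The plan itself uses inclusion of zero as the test for leaving an interval out: an interval that must contain zero adds little. That reasoning is sound, but it is stated for equal arms and then applied without comment to a 2:1 trial. When one arm is half the size of the other, a given count in the smaller arm is a larger proportion and stronger evidence of a difference. A common count of 4 is 4/300 = 1.3% on pembrolizumab but 4/150 = 2.7% on placebo. If the property fails at 2:1, the tables omit some intervals that do not meet the plan's own reason for omitting them. The safety objective in Protocol 3.2 is a comparison with placebo, so the display rule should do what its rationale says.

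**Working it through.** **Inputs.** Protocol 2.1: "Approximately 450 subjects will be randomized at a 2:1 ratio", so 450 × 2/3 = 300 and 450 × 1/3 = 150. The safety population is ASaT ("The ASaT population consists of all randomized subjects who received at least one dose of study treatment"). Treated numbers per arm are not given, so 300/150 is an assumption; smaller arms are tried below.

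**Method.** Unstratified Miettinen-Nurminen score interval with the factor N/(N-1) and critical value 1.96. At a true difference of zero the restricted estimate is the pooled proportion p, so the interval excludes zero exactly when |z| > 1.96, where

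z = (p1 - p2) / sqrt[ p(1 - p)(1/n1 + 1/n2) × N/(N - 1) ].

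**Step 1: the plan's own claim, equal arms (225/225).**
- 3 vs 0: z = 1.736, interval -0.36 to 3.85 points.
- 4 vs 0: z = 2.007, interval 0.08 to 4.49 points.

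No pair with 0 to 3 events per arm excludes zero at any of nine equal arm sizes tried from 10 to 1000. The claim reproduces, and 4 is the right cut for 1:1.

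**Step 2: the same check at 300/150.** Worked example, 0 vs 2: p = 2/450 = 0.00444; z = -0.01333 / sqrt(0.00444 × 0.99556 × 0.01 × 450/449) = -0.01333/0.00666 = -2.002.

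| Pembrolizumab vs placebo | z | 95% interval (points) | Excludes zero | Tier by count rule |
|---|---|---|---|---|
| 0 vs 1 | -1.414 | -3.68 to 0.61 | no | 3 |
| 0 vs 2 | -2.002 | -4.74 to -0.05 | **yes** | 3 |
| 0 vs 3 | -2.455 | -5.72 to -0.68 | **yes** | 3 |
| 1 vs 3 | -1.774 | -5.41 to 0.20 | no | 3 |
| 2 vs 3 | -1.271 | -5.10 to 0.77 | no | 3 |
| 3 vs 0 | 1.227 | -1.51 to 2.90 | no | 3 |
| 7 vs 0 | 1.883 | -0.19 to 4.74 | no | 2 |
| 8 vs 0 | 2.016 | 0.14 to 5.18 | yes | 2 |

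Of all pairs with 0 to 3 events per arm, only 0 vs 2 and 0 vs 3 exclude zero.

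**Step 3: why it happens.** For rare events confined to one arm, the formula reduces to z² ≈ k for k events at 1:1. At 2:1 it gives z² ≈ 2k if the events are on placebo and k/2 if they are on pembrolizumab. Setting z² above 1.96² = 3.84 requires k of at least 4 at 1:1, at least 2 on placebo at 2:1 (2 × 2 = 4), and at least 8 on pembrolizumab at 2:1 (8/2 = 4). Arm size nearly cancels, so the result is stable: the same two pairs exclude zero at 290/145, 280/140, 270/135, 200/100 and 150/75.

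**Step 4: firmness.** 0 vs 2 is borderline (Fisher p = 0.11). 0 vs 3 is firmer (Fisher p = 0.037; Newcombe interval -5.71 to -0.17 points). A Wald interval for 0 vs 3 would include zero (-4.24 to 0.24), but it is not the specified method.

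**Step 5: SAP Table 5 at 300/150.** Serious terms at 2/150 (1.3%) or 3/150 (2.0%), and Grade 3-5 terms at 3/150 (2.0%), would get an interval. Any-grade terms below 10% in both arms would not. One example is 29/300 (9.7%) vs 5/150 (3.3%), interval 1.36 to 10.78 points. The count rule would show that interval; Table 5 would not.

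**The case against.** The strongest reply is that the sentence is conditional and true: it speaks of equal groups, and for equal groups it holds. A reader might infer that the protocol makes a false statistical statement, or that it asserts omitted intervals could not exclude zero in this trial. The documents do not go that far. They give a correct reason for a different design and leave 2:1 unaddressed.

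A reader might also infer that the rule conceals safety signals against pembrolizumab. It does not. A pembrolizumab excess needs 8 vs 0 before its interval excludes zero, and that is already Tier 2. Both affected patterns have every event on placebo, one of them is marginal, and Tier 3 still reports 0% against 1.3% or 2.0%. Protocol 8.6.2 says the intervals are descriptive, unadjusted for multiplicity and not a formal test. No decision rule depends on them.

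Nor is it a defect that 4 to 7 events vs 0 are shown in Tier 2 with intervals that include zero: Tier 2 never required exclusion of zero. And equal arms are not strictly necessary for the property. With 450 subjects it still holds at 250/200 (0 vs 3, z = -1.94) and fails from about 254/196 (z = -1.98).

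Finally, if SAP Table 5 governs, the count may not decide anything. That is a fair point about what to fix, but the SAP prose and the current protocol both still carry the count rule and its reason.

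All of this limits the size of the point. What remains is that the sole rationale for the cut does not apply to this design, and that the cut fails its own criterion in two patterns.

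**Conclusion.** The point holds as a minor one. The 4-subject cut rests on an equal-arm property, the trial is 2:1, and no justification for unequal arms is given. Under the specified method, 0 vs 2 and 0 vs 3 exclude zero yet receive no interval under the count rule. The conclusion rests on the unstratified Miettinen-Nurminen interval and on 300/150 as the treated numbers; it does not change over the 2:1 arm sizes tried. It does not show that the plan misstates a fact, hides pembrolizumab toxicity, or would reach a different safety conclusion. The unresolved choice between the count rule and Table 5 is part of the same repair, because it determines which terms receive an interval at all.

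**What to change.** In Protocol 8.4.2, 8.6.2 and Table 13, and in SAP 3.4.2 and 3.5.2, replace the equal-size rationale with one that holds at 2:1 and restate the count to match. Two options work:

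- **At least 2 subjects in any group.** Simple and symmetric; it adds more rows.
- **At least 4 on pembrolizumab or at least 2 on placebo.** Fewer added rows, but they are only terms with 2 or 3 placebo events, so the newly shown zero-excluding intervals all favour pembrolizumab.

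Under either option every remaining Tier 3 interval includes zero. The pairs left are 0-1 vs 0-1 under the first and 0-3 vs 0-1 under the second; the closest to excluding zero is 0 vs 1, at -3.68 to 0.61 points.

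In the same edit, reconcile the SAP prose with SAP Table 5 so that a single rule decides which terms get an interval. Changing the count alone would have no effect if the tables are programmed from Table 5.

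The cost is a short text change in each document and a few more interval rows in the AE tables. No data collection or efficacy analysis is affected.

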8.6.3 Summaries of Demographic and Baseline Characteristics

085/RXM

The comparability of the treatment groups for each relevant characteristic will be assessed by the use of tables and/or graphs. No statistical hypothesis tests will be performed on these characteristics. The number and percentage of subjects screened, randomized, the primary reasons for screening failure, and the primary reason for discontinuation will be displayed.

Protocol/Amendment No.: 394-06

Demographic variables (e.g., age), baseline characteristics, primary and secondary diagnoses, and prior and concomitant therapies will be summarized by treatment either by descriptive statistics or categorical tables.

8.7 Interim Analyses

An external data monitoring committee (eDMC) will be convened to review the unblinded efficacy results and accumulating safety at the planned IAs.

8.7.1 Efficacy Interim Analyses

Two interim analyses and one final analysis are planned in this trial. The timing and the purpose of each analysis are summarized in Table 14. A detailed description of the multiplicity adjustment and hypotheses testing plan is provided in Section 8.8 Multiplicity.

The first interim analysis will be performed at approximately Month 17, at which time the first 163 randomized subjects have at least 24 weeks follow-up. The main purpose of this interim analysis is to conduct the analysis for ORR on the first 163 randomized subjects, evaluate the consistency of efficacy and safety in this study to the reference global data, and to conduct an interim testing for efficacy on the PFS and OS endpoints for all the subjects randomized at that time (superiority only). Consistency of efficacy will be evaluated by comparing the treatment effect observed in this study to the reference global data (based on point estimates). Approximately 225 subjects will be enrolled at the first interim analysis cutoff, with approximately 174 PFS events and 100 OS events projected to be accumulated. The main purpose of the second interim analysis is to conduct the primary testing for efficacy on the PFS hypothesis and to conduct an interim testing for efficacy on the OS hypothesis (superiority only). It will be performed when enrollment is complete and approximately 276 OS events (~80% of the target 345 total OS events) are observed. It is projected that this event count will be accumulated at approximately 31 months after the start of the study. Approximately 395 PFS events are expected to be accumulated by then. Under assumptions specified in Section 8.9 sample size and power calculation, at the time of the secondary interim analysis: 1) a total of approximately 395 PFS events for testing the PFS hypothesis at Type I error α=0.2% provides approximately 88% power to successfully demonstrate the PFS hypothesis; and 2) a total of approximately 276 OS events for testing the OS hypothesis at Type I error α =1.10% provides approximately 70% power to successfully demonstrate the OS hypothesis.

If superiority of PFS or OS (pembrolizumab vs. placebo) is demonstrated at one of the interim analyses, the ORR hypothesis will be tested according to the group-sequential boundaries for ORR analysis (see Table 17 in Section 8.8 Multiplicity).

The final analysis (FA) will be performed when approximately 345 OS events are observed which is expected at Month 37.

Protocol/Amendment No.: 394-06

Table 14 Summary of Interim and Final Analyses Strategy

Analysis	Endpoint(s)	Criteria for Conduct of Analysis	Estimated Time after First Subject Randomized	Primary Purpose of Analysis
IA 1	ORR, DOR, PFS, OS	First 163 randomized subjects have at least 24 weeks follow-up	~17 months	Descriptive ORR analysis, consistency evaluation
IA 2	ORR, PFS, OS	~276 OS events observed	~31 months	PFS FA OS IA
FA	OS, ORR	~345 OS events observed	~37 months	OS FA

Abbreviations: FA = final analysis; IA = interim analysis; PFS = progression-free survival; ORR = overall response rate; OS = overall survival

The eDMC will serve as the primary reviewer of the unblinded results of the interim analyses and will make recommendations. Depending on the recommendation of the eDMC, the Sponsor may prepare a regulatory submission. NOTE: no futility test is planned in the interim analysis.

